2. LIST OF ABBREVIATIONS

Term	Definition / description
AE	Adverse event
BI	Boehringer Ingelheim
BIBW 2992	Afatinib
BMI	Body mass index
BSA	Body surface area
CR	Complete response
CTCAE	Common Terminology Criteria for Adverse Events
CTP	Clinical Trial Protocol
DLT	Dose limiting toxicity
EMA	European Medicines Agency
ICH	International Conference on Harmonisation
IPV	Important protocol violation
MedDRA	Medical Dictionary for Regulatory Activities
MGMT	O ⁶ -methylguanine-DNA methyltransferase
NCI	National Cancer Institute
PK	Pharmacokinetics
PR	Partial response
PT	Preferred term
RT	Radiotherapy
SAE	Serious adverse event
SD	Standard deviation
SIAE	Significant adverse event
SOC	System Organ Class
TMZ	Temozolomide
TSAP	Trial statistical analysis plan

3. INTRODUCTION

As per International Conference on Harmonisation (ICH) E9, the purpose of this document is to provide a more technical and detailed elaboration of the principal features of the analysis described in the protocol, and to include detailed procedures for executing the statistical analysis of the primary and secondary variables and other data.

This Trial Statistical Analysis Plan (TSAP) assumes familiarity with the Clinical Trial Protocol (CTP), including Protocol Amendments. In particular, the TSAP is based on the planned analysis specification as written in CTP Section 7 “Statistical Methods and Determination of Sample Size”. Therefore, TSAP readers may consult the CTP for more background information on the study, e.g., on study objectives, study design and population, treatments, definition of measurements and variables, planning of sample size, randomisation.

SAS® Version 9.2 (or later version) will be used for all analyses.

4. CHANGES IN THE PLANNED ANALYSIS OF THE STUDY

See statistical changes described in:

- Protocol amendment 3, dated 07 February 2011 ([1](#)).

In addition the following changes were not documented in CTP amendments.

Section 7.3.3 of the CTP states:

In-depth analyses will describe the onset, CTCAE grades, duration and clinical consequences of:

- *Diarrhoea;*
- *Nausea and vomiting;*
- *Rash and acne;*
- *Worsening of cardiac left ventricular function;*
- *Worsening of laboratory abnormalities;*
- *Other AEs that occur with sufficient overall frequency (>10%).*

However project defined special grouped-term search categories have not been identified for either worsening of cardiac left ventricular function or laboratory abnormalities as reported adverse events (AEs), therefore in-depth analyses will not be performed as described above. Instead, descriptive statistics are planned for left ventricular ejection fraction which will include worst value on treatment and change from baseline. Furthermore, clinically significant laboratory abnormalities will be analysed according to Boehringer Ingelheim (BI) standards. Also, dependent on the final sample size, it is possible that all AEs will occur with frequency >10%; thus the other AEs that will be analysed in-depth will be determined pragmatically by the trial team.

5. ENDPOINTS

5.1 PRIMARY ENDPOINTS

Investigator defined dose limiting toxicity during concomitant treatment period:

At least one AE meeting the criteria for dose limiting toxicity (DLT; as determined by the investigator and defined in Section 5.2.3 of the CTP) with onset during the 42 day concomitant treatment period when trial medication is given concomitantly with radiotherapy (RT).

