### 5.2.4 Maximum Tolerated Dose (MTD)

7. The MTD is defined as:
8. The dose of BIBW 2992 when given concomitantly with TMZ and RT (Regimen M) or BIBW 2992 when given concomitantly with radiotherapy (Regimen U) which is one dose tier below that dose at which two or more out of six patients experienced drug-related DLTs during the 6 weeks (42-day) RT treatment period. DLT experienced after the start of the maintenance treatment period will be examined separately. At the MTD, no more than one patient out of six patients may experience DLT, i.e., MTD is defined as the

highest dose studied for which the incidence of DLT is no more than 17% (i.e. 1/6 patients).

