7.4 PRIMARY ENDPOINTS

DLT during concomitant treatment period:

The analysis of the primary endpoint will summarise DLT using descriptive statistics with the aim of determining the maximum tolerated dose (defined in Section 5.2.4 of the CTP) of:

- Afatinib in combination with TMZ when given concomitantly with RT (Regimen M);
- Afatinib when given concomitantly with RT (Regimen U).

An overall summary of AE occurrences with onset during the concomitant treatment period, which were defined to be DLTs by the investigator, will be presented. This will include the following AE attributes:

- Preferred term,
- Maximum CTCAE grade,
- Outcome,
- Time to first occurrence (relative to start of trial medication; see [Section 9.2](#) of this document).

Any AE meeting the criteria for DLT, regardless of date of onset, will be considered a significant adverse event (SIAE). The analysis of non-serious SIAEs and serious adverse events (SAEs) is described in [Section 7.8.1](#) of this document.

DLTs with onset after the concomitant treatment period will be listed separately.

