7.8 SAFETY ANALYSIS

7.8.1 Adverse events

The analyses of AEs will be descriptive in nature. All analyses of AEs will be based on the number of patients with AEs (not the number of AEs). For this purpose, AE data will be combined in a 2-step procedure into AE records.

In a first step, AE occurrences, i.e. AE entries on the case report form, will be collapsed into AE episodes provided that all of the following applies:

- The same Medical Dictionary for Regulatory Activities (MedDRA) lowest level term was reported for the occurrences,
- The occurrences were time-overlapping or time-adjacent (time-adjacency of 2 occurrences is given if the second occurrence started on the same day or on the day after the end of the first occurrence),
- Treatment did not change between the onset of the occurrences or treatment changed between the onset of the occurrences, but no deterioration was observed for the later occurrence.

In a second step, AE episodes will be condensed into AE records provided that the episodes were reported with the same term on the respective MedDRA level and that the episodes are

assigned to the same treatment. For further details on summarisation of AE data, please refer to BI standards for AEs. (5)

CTCAE grade and investigator-defined DLT will be included as additional AE attributes. For the purposes of collapsing, additional deterioration rules will be defined for both attributes. In addition, in this trial, the standard AE attribute 'action taken with trial drug' is separated for afatinib and TMZ; the standard condensing rules will be applied for both.

The analysis of AEs will be based on the concept of treatment emergent adverse events. That means that all AEs occurring between first administration of trial medication until 28 days after last administration of trial medication will be assigned to trial medication. All AEs occurring before first administration of trial medication will be assigned to 'screening' and all AEs occurring after last administration of trial medication + 28 days will be assigned to 'post-study'.

Any AE meeting the criteria for DLT (defined in Section 5.2.2 of the CTP), regardless of date of onset, will be considered an SAE or SIAE.

According to ICH E3 (6), AEs classified as 'other significant' will include those non-serious and non-significant AEs:

- (i) with 'action taken = discontinuation' or 'action taken = reduced', or

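### The SAP places a DLT in the radiotherapy period by the onset of the adverse event, so an event that first reaches DLT grade in maintenance can enter the count behind the reported MTD

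*SAP*

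**What the plan says.** **SAP.** The primary endpoint in SAP 5.1 is at least one adverse event that meets the DLT criteria, "with onset during the 42 day concomitant treatment period when trial medication is given concomitantly with radiotherapy (RT". SAP 7.4 makes the selection concrete. It summarises "AE occurrences with onset during the concomitant treatment period, which were defined to be DLTs by the investigator", and adds that "DLTs with onset after the concomitant treatment period will be listed separately". An event is therefore selected on two conditions: onset in the RT period, and an investigator DLT flag. Neither section says on which day the DLT criteria must be met.

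**Protocol.** Section 5.2.4 defines the MTD from DLTs that patients experience during the 42-day RT period, and states: "DLT experienced after the start of the maintenance treatment period will be examined separately". At the MTD no more than one of six patients may have a DLT (17%). SAP 7.4 summarises DLTs "with the aim of determining the maximum tolerated dose (defined in Section 5.2.4 of the CTP", so it relies on this definition while splitting the periods by onset.

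**Doses and records.** Planned maintenance is 40 mg in both regimens, whatever the dose during RT (protocol 4.1.3 and 4.1.4.1). After a dose reduction in RT, the maintenance dose is decided case by case (4.1.4.1.2). DLTs can be identified in any treatment cycle (4.1.4.1.2). Protocol 5.2.1 names an onset date, an end date and a CTCAE grading for each AE. It names no date of grade change.

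**The concern.** Take a patient in the 20 mg cohort whose Grade 1 diarrhoea starts on Day 30. RT ends, the patient moves to 40 mg, and on Day 55 the diarrhoea first reaches Grade 3 and goes on to meet the DLT criterion. By protocol 5.2.4 this DLT was experienced in maintenance and is examined separately. If the site keeps one CRF entry, SAP 5.1 and 7.4 see an onset on Day 30 and a DLT flag, and count it against 20 mg with RT.

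The path is plausible. Protocol 1.2.1 describes diarrhoea and skin events as dose dependent, and patients in the 20 and 30 mg cohorts are planned to step up after RT. The MTD limit is 1/6, so where a cohort of six already has one genuine RT-period DLT, a single misplaced event takes it over the limit.

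Timing limits where the harm falls. Escalation is decided once the cohort has completed six weeks (4.1.4.1.1), when most such worsening has not yet happened. The MTD may be determined at a snapshot after the last cohort finishes RT (7.3.4). By then the lower-dose cohorts may have been on maintenance for some time. Their RT-period counts could grow after they had cleared, and would depend on the data cut.

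**Working it through.** **Plan's own figures.** 1/6 = 16.7%, the protocol's 17%. 2/6 = 33.3%, over the limit. Both agree with protocol 5.2.4.

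**Inputs.** *n* = 6 and the limit of 1/6 come from protocol 5.2.4. Two rates are assumptions, because the documents give neither:
- *p* = true probability of a DLT in the RT period, set at 0.10;
- *q* = probability that an event starts at low grade in RT, stays one CRF entry, and first reaches DLT grade in maintenance, set at 0.01 to 0.10.

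The two are taken as independent, and patients as independent of each other.

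**Step 1. Probability of being counted under onset dating.** p* = 1 − (1 − p)(1 − q). For q = 0.05, p* = 1 − 0.90 × 0.95 = 0.145.

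**Step 2. Chance of at most 1/6.** P = (1 − p*)^6 + 6p*(1 − p*)^5. With q = 0: 0.5314 + 6 × 0.10 × 0.5905 = 0.886.

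| q | p* | P(at most 1/6) | Fall from 0.886 |
|---|---|---|---|
| 0 | 0.100 | 0.886 | none |
| 0.01 | 0.109 | 0.868 | 0.018 |
| 0.02 | 0.118 | 0.849 | 0.037 |
| 0.05 | 0.145 | 0.788 | 0.098 |
| 0.10 | 0.190 | 0.680 | 0.206 |

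**Step 3. What it takes to cross the limit.** Given one genuine DLT among six, the chance that at least one of the other five adds a late-worsening event is 1 − (1 − q)^5: 0.049, 0.096, 0.226 and 0.410 for q = 0.01, 0.02, 0.05 and 0.10. Given none among six, two late events are needed: 1 − (1 − q)^6 − 6q(1 − q)^5 = 0.001, 0.006, 0.033 and 0.114. The exposure is mainly in cohorts that already stand at 1/6.

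**Step 4. Same data, two rules.** A cohort with one RT-period DLT and one late-worsening event stands at 2/6 by AE onset. It stands at 1/6 when the DLT is dated by the day it reaches qualifying grade.

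**The case against.** The strongest reply is that the SAP can be read consistently with the protocol. The endpoint is labelled DLT during the concomitant period, onset might mean onset of the DLT, and the MTD is taken from protocol 5.2.4. Protocol 7.3.1 itself tabulates events by study period and day at onset. This stands in part: protocol 7.3.1 needs reconciling too. But SAP 7.4 attaches onset to the AE occurrence and makes the DLT flag a separate condition, and protocol 7.3.1 describes a table rather than defining the MTD count.

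Second, the error needs the worsening to stay in the same CRF entry. SAP 7.8.1 defines an occurrence as a CRF entry. If a rise in grade opens a new entry, its onset falls in maintenance and SAP 7.4 lists it separately. This stands as a condition: the documents do not say how grade changes are entered.

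Third, a reader might infer that collapsing always merges such events. SAP 7.8.1 allows merging where "Treatment did not change between the onset of the occurrences or treatment changed between the onset of the occurrences, but no deterioration was observed", and also says that "all AEs occurring between first administration of trial medication until 28 days after last administration of trial medication will be assigned to trial medication". RT and maintenance might then look like one treatment, so that deterioration rules never act between them. The documents do not support that. The primary summary uses occurrences, before collapsing. Additional deterioration rules for grade and DLT flag are promised but not spelled out, and the sponsor standard cited for further detail is not among the documents. What can be said is that those rules may not act at this boundary unless the SAP says so.

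**Conclusion.** The concern holds in a limited form. SAP 5.1 and 7.4 date by AE onset, protocol 5.2.4 by when the DLT is experienced, and the two are not reconciled. Followed literally, the SAP can move a maintenance DLT into the RT count. The dose is misattributed only for the 20 and 30 mg cohorts. At 40 mg the planned dose is the same and only the period is wrong.

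On the assumptions above, the chance of observing at most 1/6 falls by about 2, 4, 10 or 21 percentage points for q of 1%, 2%, 5% or 10%. At the low end this is minor. These figures assume that every such event is kept as one entry dated from its first onset.

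A reader might infer two stronger things. One is that escalation would be misdirected; protocol 4.1.4.1.1 sets that decision at six weeks, so it is largely untouched. The other is to take the chance of any misplaced patient among six, 1 − (1 − q)^6 = 0.26 at 5% and 0.47 at 10%, as the chance of a changed MTD. It is not, because one misplaced event changes the result only when the cohort already stands at the limit.

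**What to change.** 1. In SAP 5.1 and 7.4, assign each DLT to a period by the first day the event is at the DLT-qualifying grade. An event at that grade in RT whose duration condition is met later stays in RT.
2. Say where the date comes from. DLTs are significant AEs and are reported immediately on the sponsor's SAE form (protocol 5.2.5 and 8.4.1). Use that report, or a query to the site, where the eCRF lacks the date. The documents do not state that the form holds it.
3. Reconcile the wording with protocol 5.2.4 and with the onset-based table in 7.3.1. Onset can stay as a descriptive column.
4. In SAP 7.8.1, state that the promised deterioration rules for grade and DLT flag also apply across the boundary between RT and maintenance.

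The cost is SAP wording, a small amount of programming and possibly one site query per DLT. No new visit or assessment is needed.

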5.2 SECONDARY ENDPOINTS

5.2.1 Key secondary endpoints

This section is not applicable as no key secondary endpoints have been specified in the CTP.

5.2.3 (Other) Secondary endpoints

Adverse events:

[figure not shown]
Maximum grade (severity) of AEs according to the United States National Cancer Institute (NCI) Common Terminology Criteria for Adverse Events (CTCAE) version 3.0.

Objective response:

Best overall response of complete response (CR) or partial response (PR), where best overall response is the best overall response to trial medication (without clinical disease assessment) according to the Macdonald criteria (defined in Section 5.1.3 of the CTP) recorded since first administration of trial medication and until disease progression or start of further anti-cancer treatment.

Pharmacokinetic (PK) parameters:

The derivation of standard PK parameters is performed according to BI standards. (2)

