#### 5.1.3 Tumour assessment

Response will be evaluated according to the Macdonald criteria (R08-1053):

Complete Response (CR): Disappearance of all enhancing tumour on consecutive MRI scans at least 28 days apart, off steroids, and neurologically stable or improved.

Partial Response (PR): At least 50% reduction in size of enhancing tumour on consecutive MRI scans at least 28 days apart, steroids stable or reduced, and neurologically stable or improved.

Progressive Disease (PD): a) at least 25% increase in size of enhancing tumour or  
b) any new tumour on MRI scans or  
c) unequivocal neurological deterioration (due to underlying tumour progression and not due to co-morbid event or concurrent medication) with steroids being stable or increased.

Stable Disease (SD): All other situations

‘Size’, will be defined as the tumour’s largest cross-sectional area. Multifocal lesions are defined as PD if any measurable lesion increases by >25%, or if there is an assessment of any evaluable lesion(s) as progressive.

‘Unequivocal neurological deterioration’ will be assessed locally by each investigator. The clinical decline must be attributed to the underlying tumour progression and not due to co-morbidity or concomitant medication.

Objective tumour response rate is defined as the sum of all CRs and PRs as a fraction of all patients. For a detailed time schedule of tumour assessment please refer to the Flow Chart and Section 6 of this protocol.

Pseudo-progression based on imaging parameters only is a common phenomenon in GBM patients after prior radiotherapy. In order to avoid labelling progressive enhancement or oedema which develops immediately after the end of RT as tumour progression, treatment should not be delayed or stopped within 3 months of RT as suggested by the “Canadian GBM Recommendations committee” (R09-6378)

If a patient shows radiological progression on his/her first scan occurring within 2 months post RT, the patient should not stop study medication and be removed from the study. Instead, the patient should stay on the study until the second MRI scan (scheduled at 4 months post RT) confirms the patient has progressed or not. If the course of events shows that true progression indeed occurred, the date of the first increase in tumor size is to be considered as the date of progression.

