The sponsor may remove patients from the study, after approval of amendment 5, if the patients have access to BIBW 2992 (Afatinib) through marketed product, an expanded-access program, named patient use program, compassionate use protocol or other means based on local regulation. If a patient is removed from the study, an end of treatment and follow up visit will need to be performed to ensure all adverse events are followed up. The cost of any on-going supply of BIBW 2992 (Afatanib) will be incurred by the Sponsor.

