## **7.3.2 Secondary analyses**

### **7.3.2.1 Tumour response**

Tumour response for each patient will be assigned according to the Macdonald criteria as specified in Section 5.1.3. Objective tumour response is defined as complete response (CR) or partial response (PR).

Tumour response according to the separate components of the MacDonald criteria (CR, PR, SD or PD) will be tabulated by treatment regimen and dosage cohort according to the patient's best response during the study.

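### The SAP scores objective response without clinical assessment while citing protocol criteria that require it, and does not declare the change

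*SAP*

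**What the plan says.** Protocol section 5.1.3 defines CR as "Disappearance of all enhancing tumour on consecutive MRI scans at least 28 days apart, off steroids, and neurologically stable or improved". PR needs at least a halving of the enhancing tumour on consecutive scans, with "steroids stable or reduced, and neurologically stable or improved". Unequivocal neurological deterioration due to the tumour, with steroids stable or increased, is one route to PD. The remainder is covered by "Stable Disease (SD): All other situations".

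Protocol section 7.3.2.1 carries this into the analysis: "Tumour response for each patient will be assigned according to the Macdonald criteria as specified in Section 5.1.3". The categories "will be tabulated by treatment regimen and dosage cohort according to the patient's best response during the study".

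SAP section 5.2.3 defines objective response as a best overall response of CR or PR, where "best overall response is the best overall response to trial medication (without clinical disease assessment) according to the Macdonald criteria". The same sentence cites protocol section 5.1.3 and closes the window at progression or when further anti-cancer therapy starts. SAP section 7.5.2 adds only that the analysis is descriptive.

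SAP section 4 refers to protocol amendment 3 and continues: "In addition the following changes were not documented in CTP amendments". What follows concerns only the in-depth safety analyses of protocol section 7.3.3.

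**The concern.** The SAP sentence invokes a definition and sets part of it aside. The clinical conditions are part of what makes a response CR or PR in protocol section 5.1.3, so a rate derived without them is not the protocol's endpoint even if it carries the Macdonald name.

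Two things are at stake. First, the parenthesis is undefined in the visible text, so two programmers could derive different response rates from the same data. Second, objective response is the only efficacy criterion in the synopsis, and protocol section 7.1 says preliminary therapeutic effects will help identify the dose for future studies. A reader of the report would take a Macdonald response rate to include the clinical conditions.

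The conditions can matter in this population. Inclusion criterion 6 admits patients on corticosteroids, and protocol section 10.6 allows steroids during radiotherapy for progressive neurological deficit.

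**Working it through.** There is no planned figure to reproduce: response has no hypothesis test, no target rate and no sample size based on it. The check is a comparison of texts, followed by simple arithmetic.

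**1. What the parenthesis removes.** Protocol section 5.2.7 describes the physical examination, with emphasis on neurological status, as a clinical assessment of the tumour. That makes the neurological condition the natural target. Steroid use is not mentioned. This leaves two readings: (A) only the neurological elements are dropped; (B) the steroid conditions are dropped as well. Both are taken to set aside the neurological route to PD.

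**2. Classification of a confirmed scan response under each rule.**

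| Scans | Steroids | Neurological status | Protocol 5.1.3 | SAP, reading A | SAP, reading B |
|---|---|---|---|---|---|
| At least halved | Stable or reduced | Not worse | PR | PR | PR |
| At least halved | Stable or reduced | Worse, PD clause not met | SD | PR | PR |
| At least halved | Stable | Unequivocal decline from tumour | PD | PR | PR |
| At least halved | Increased | Not worse | SD | SD | PR |
| Enhancement gone | Continuing, stable dose | Not worse | PR | PR | CR |

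Rows 2 and 3 become responders under either reading, and row 4 only under B. The last row fails CR but still meets PR in the protocol, so only the category changes and the responder count does not.

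**3. Direction.** With the scans and the response window held fixed, removing conditions from CR and PR can only leave the responder count unchanged or raise it. The net difference from the protocol's rate is not established, because the windows differ: the SAP stops at progression or further anti-cancer therapy, while protocol section 7.3.2.1 uses the best response during the study.

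**4. Whether the change is declared elsewhere.** The SAP's pointer to amendment 3 does not cover it. The current protocol is later than that amendment, since section 6.3 contains "The sponsor may remove patients from the study, after approval of amendment 5", and its sections 5.1.3 and 7.3.2.1 still hold the full criteria.

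**5. Size per patient.** Protocol section 5.1.3 takes the rate over all patients, and SAP section 7 reports whole-number percentages. One reclassified patient changes the rate by 1/n:

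- n = 3 (initial cohort, protocol section 4.1.4.1.1): 1/3 = 33.3, about 33 points
- n = 6 (expanded after a DLT, same section): 1/6 = 16.7, about 17 points
- n = 12 (expanded MTD cohort, same section): 1/12 = 8.3, about 8 points
- n = 30 (maximum per regimen, synopsis): 1/30 = 3.3, about 3 points

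The documents give no frequency for scan responses that fail a clinical condition, so the number of reclassified patients cannot be derived.

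**The case against.** The strongest counter-argument is that the phrase is ambiguous. It could mean that the analysis takes the Macdonald response as recorded, with the clinical conditions already applied, and leaves out only some separate, purely clinical judgement. On that reading no CR or PR condition is lost and section 4 has nothing to declare. Parts of the SAP are also blacked out, and a definition could sit there.

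Both points stand as limits on certainty about what is dropped. Neither removes the problem. The operative sentence is intact and appears to conflict with the section it cites, section 4 is legible and silent on response, and on the benign reading the parenthesis does nothing for CR and PR and can go.

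It is also fair that the steroid provisions cited concern the period before treatment and during radiotherapy, whereas on-treatment scans fall in the maintenance phase. They show that the conditions can matter, not how often. Likewise, the 1/n figures apply to any reclassification of one patient.

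Finally, the plan makes no comparison between cohorts or regimens. That limits the consequence and is reflected in the weight given below.

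The practical objection has most force: no visible text shows that neurological status relative to baseline is recorded at the response scans, and protocol section 5.1.3 assigns local investigator judgement only to the deterioration clause of PD. The fix has to allow for this.

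**Conclusion.** The concern holds. SAP section 5.2.3 departs, on its most natural reading, from the definition it cites, and SAP section 4 does not declare it. Followed as written, the SAP could report a protocol SD or PD patient as a Macdonald responder. Each such patient shifts a cohort's rate by about 8 to 33 points, depending on cohort size; how many there would be is unknown.

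This rests on two assumptions: that the parenthesis refers at least to the neurological condition, and that no blacked-out text defines it otherwise. Whether the steroid conditions are also dropped remains open.

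The endpoint is descriptive and secondary and the MTD does not depend on it, so this should be corrected but does not threaten the trial's primary result.

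**What to change.** Delete the parenthesis in SAP section 5.2.3 and derive CR and PR by all the conditions of protocol section 5.1.3, using the recorded steroid data and the investigator's neurological assessment.

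Before doing so, confirm that the eCRF captures the baseline steroid dose and the neurological status at the response scans. Steroid data should exist: concomitant medication is documented at Screening Visit 2, and protocol section 4.2 requires dose and dates. Tumour assessment accompanies each MRI, and a physical examination is scheduled at each maintenance cycle visit. If the neurological judgement is not in the eCRF, obtain it from the investigator's source records or state the limitation in the report.

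If an imaging-only rate is wanted, present it as an additional summary, labelled as such, naming the omitted components, and declare it in SAP section 4.

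The cost is a wording change and some extra derivation work, plus source retrieval if the eCRF has a gap. The rate may show fewer responders.
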